3.3.3 Safety and Tolerability Variables

Module 1 – Part A

The primary objective of Part A is to assess the safety and tolerability, describe the DLTs, and identify the MTD and/or RP2D of AZD4573 in combination with acalabrutinib (100mg BID) in subjects with relapsed/refractory DLBCL or MZL.

Data from all cycles of treatment will be combined in the presentation of safety data.

An overall summary table of the number of subjects experiencing each category of adverse events will be produced.

The number of subjects experiencing treatment emergent adverse events by MedDRA system organ class (SOC) and MedDRA preferred term (PT) will be presented, with further splits by CTCAE grade, causal relationship to study medication and adverse events classed as Grade 3 or higher.

Separate tables will present dose limiting toxicities, adverse events leading to discontinuation, serious adverse events (SAES) and other significant adverse events. All AE data will be listed appropriately.

AEs occurring prior to first dose of investigational product (ie, before study Day 1) which subsequently worsen in severity following dosing will be presented in the summary tables. All other AEs occurring prior to first dose of investigational product (ie, before study Day 1), or after the 30-day follow-up period after discontinuation of investigational product will be listed separately, but not included in the summaries.

Module 1 – Part B

The secondary objective of Module 1 Part B is to assess the safety and tolerability of the RP2D of AZD4573 in combination with acalabrutinib (100 mg BID) in subjects with relapsed or refractory DLBCL with GCB or non-GCB subtype.

The following assessments will be performed:

- Adverse event (AE) assessments
- Dose limiting toxicities (DLTs) defined in [Section 4.11.3](#)
- Clinical laboratory tests described in [Section 4.11.6](#)
- Vital signs (systolic blood pressure [SBP] and diastolic blood pressure [DBP], pulse rate, oral body temperature), height and weight
- 12-lead Electrocardiograms (ECG)
- Tumor lysis syndrome (TLS)
- B symptoms (unintentional weight loss, fevers and night sweats)
- Eastern Cooperative Oncology Group performance status (ECOG PS)
- Left ventricular ejection fraction (echocardiograms [ECHO] / multi-gated acquisition scan [MUGA])
- Physical examinations

The full list of laboratory measurements performed during the study that are used to evaluate safety and tolerability variables can be found in [Section 4.11.6](#).

Module 2

The secondary objective of Module 2 is to assess the safety and tolerability of the RP2D of AZD4573 in combination with acalabrutinib (100 mg BID) in subjects administered AZD4573 monotherapy and to confirm the RP2D of AZD4573 monotherapy in MCL.

The following assessments will be performed:

- Vital signs (blood pressure, pulse rate, temperature)
- 12-lead Electrocardiogram (ECG)
- Clinical laboratory tests (haematology, clinical chemistry, coagulation, urinalysis parameters, CD4, CD8, CD19, CD16/NK, cardiac troponin I or troponin T measurements, electrolyte panel, supra-renal glands and Lipase and amylase measurements)
- Adverse event (AE) assessments
- Dose modifications
- Tumour lysis syndrome (TLS)
- B symptoms (unintentional weight loss, fevers and night sweats)
- Eastern Cooperative Oncology Group performance status (ECOG PS)
- Left ventricular ejection fraction (echocardiograms [ECHO] / multi-gated acquisition scan [MUGA]).

4 STATISTICAL METHODS

4.1 Data Quality Assurance

All tables, figures and listings to be included in the report will be independently checked for consistency, integrity and in accordance with standard Parexel procedures.

4.2 General Presentation Considerations

The following considerations will be applicable to all modules.

Continuous data will be summarised in terms of the mean, standard deviation (Std Dev), median, 25th and 75th percentiles (where appropriate), minimum, maximum and number of observations. If data are available for less than 3 subjects, no summary statistics other than minimum, maximum and number of observations will be presented. For log--transformed data it is more appropriate to present geometric mean (gmean), geometric coefficient of variation (CV), median, minimum and maximum.

Categorical data will be summarised by frequency counts and percentages for each category.

Percentages will be presented to one decimal place. Percentages will not be presented for zero counts. Unless otherwise stated, percentages will be calculated out of the analysis set total and each dose level/cohort.

Confidence intervals (CIs), when presented, will generally be constructed at 2-sided 80% and 95% level. CIs will be presented to one additional place than the original data. When presented, P-values greater than or equal to 0.001, in general, will be presented to three decimal places. P-values less than 0.001 will be presented as “<0.001”.

For continuous data, descriptive summary statistics (mean, median, quartiles, Std Dev, standard error, confidence intervals [CIs]) will be rounded to 1 additional decimal place compared to the original data. Minimum and maximum will be displayed with the same accuracy as the original data.

For categorical data, percentages will be rounded to 1 decimal place. In Module 1, summary tables will be presented by dose level combining Module 1 Part A and Module 1 Part B subjects unless otherwise stated. Data from RP2D-treated Module 1 Part A subjects that meet entry criteria for Module 1 Part B will also be included in Module 1 Part B.

A subgroup analysis will be performed. For the purposes of recycling of data from Module 1 Part A subjects for analysis with Module 1 Part B subject data, cell of origin (COO data) from local assessment will be used. The histology subtype was assigned by local sites, and it was confirmed by central laboratory only for subset of GCB and non-GCB subjects were treated at RP2D (AZD4573 12 mg) and all Module 1 Part B subjects.

Efficacy endpoints may also be summarised by other relevant subgroups (eg, Lymphoma classification, Histology subtype, prior anti-cancer therapies [CAR-T, BiTE and BTKi]).

Generally, the last observation prior to the first dose of the study treatment, will be considered the baseline measurement. For non-numeric laboratory tests (ie some of the urinalysis parameters) where taking an average is not possible then best value would be taken as baseline as this is the most conservative. In the scenario where there are two assessments on day 1, one with time recorded and the other without time recorded, the one with time recorded would be selected as baseline (if it is earlier than the start time of study treatment). Where safety data are summarised over time, study day will be calculated in relation to date of first dose.

For assessments on the day of first dose where time is not captured, a nominal pre-dose indicator, if available, will serve as evidence that the assessment occurred prior to first dose. Assessments on the day of first dose where neither time nor a nominal pre-dose indicator are captured will be considered prior to first dose if such procedures are required by the protocol to be conducted before first dose.

Change from baseline will be calculated as the post-dose value minus the baseline value as:

$$\text{post-baseline value} - \text{baseline value}$$

Percent change from baseline will be calculated as:

$$\frac{\text{post-baseline value} - \text{baseline value}}{\text{baseline value}} \times 100$$

Visit naming conventions are defined separately for efficacy and non-efficacy data.

Visits for efficacy summaries will be named according to the time from first dose as defined in the CSP. Examples are:

- After 8 weeks
- After 17 weeks
- After 26 weeks

All other data will follow the following naming conventions:

- Cycle 1 (ramp-up):
 - Cycle 1 6 mg AZD4573 dose x
 - Cycle 1 9 mg AZD4573 dose x
 - Cycle 1 12 mg AZD4573 dose x
 - “x” is replaced with “1”, “2”, “3”, etc. as applicable, and refers to the count of the dose received at that specified amount.
- Cycle 2 onwards:
 - Cycle 2 Day 1
 - Cycle 2 Day 8
 - Cycle 2 Day 15
 - Cycle 3 Day 1
 - That is, the visit name as per schedule of activities in the CSP is followed.

4.3 General Variables

4.3.1 Study Day Definitions

Study day 1 is defined as the date of first dose of Investigational Product (IP) (Cycle 1 Day 1).

For visits (or events) prior to first dose, study day is defined as (date of visit [event] – date of first dose of IP). For visits (or events) that occur on or after first dose of IP, study day is defined as (date of visit [event] – date of first dose of IP + 1). There is no study day 0.

“Days since last dose” is defined as (event date – date of last dose) where “date of last dose” is defined as the date of dosing immediately preceding the event occurrence. Thus, events on the same day as the last dose will be described as occurring zero days from last dose of IP.

4.3.2 Visit Window

For safety and tumour assessments, visit windows will be defined for any presentations that summarise values by visit. The following conventions will apply:

For tumour assessments:

- The protocol assigned windows for tumour assessments will be used to assign the result to a particular visit.
- For example, the visit windows for tumour assessments are:
 - After 8 weeks: 49-63
 - After 17 weeks: 112-126
 - After 26 weeks: 175-189

For safety assessments:

- The time windows will be exhaustive so that data recorded at any timepoint has the potential to be summarised. Inclusion within the time window will be based on the actual date and not the intended date of the visit.
- All unscheduled visit data will have the potential to be included in the summaries.
- The window for the visits following baseline will be constructed in such a way that the upper limit of the interval falls halfway between the two visits (the lower limit of the first post-baseline visit will be Day 2). If an even number of days exists between two consecutive visits then the upper limit will be taken as the midpoint value minus 1 day.
- For example, the visit window for AZD4573 administration (with 1 week between scheduled visits) are:
 - Cycle 1 6 mg AZD4573 Dose 1:1
 - Cycle 1 9 mg AZD4573 Dose 1: 2-11
 - Cycle 1 12 mg AZD4573 Dose 1: 12-18
 - Cycle 1 12 mg AZD4573 Dose 2: 19-25
 - Cycle 1 12 mg AZD4573 Dose 3: 26-32

- If dose delays are experienced, the planned dosing visit windows will be modified during the programming to anchor to the actual visit date where intervention was administered on to adjust for these dose delays. The same rules apply to safety visits of other types (non-dosing visits) where the safety visit is moved due to a dose delay. For example, if the Day 8 dose is taken on Day 10, the visit windowing will be anchored around Day 10 for this visit.
- Visit windowing will be done separately for each assessment based on the schedule of events specific to that assessment.
- Should Study Day be missing (due to partial or missing dates), then visit will be assigned to the nominal visit at which that assessment was recorded, and no windowing will be performed.
- For summaries showing the maximum or minimum values, the maximum/minimum value recorded on treatment (from the day of the first IP administration up to the day of the last IP administration) will be used (regardless of where it falls in an interval).
- Listings should display all values contributing to a time point for a subject.
- If multiple measurements are taken on the same day, due to inappropriate procedures or any other issues with the first measurement, the reassessment measurement on that day will take preference for analysis, should the values for that day be in the analysis after visit windowing rules have been applied.
- If there are more than one value per subject within a time window then the closest value to the scheduled visit date should be summarised, or the earlier, in the event the values are equidistant from the nominal visit date. The listings should highlight the value for the subject that contributed to the summary table, wherever feasible. Note: in summaries of extreme values all post baseline values collected are used including those collected at unscheduled visits regardless of whether the value is closest to the scheduled visit date.

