4.11.4 Adverse Events

Adverse Events (AEs) will be coded using the Medical Dictionary for Regulatory Activities (MedDRA) Version 24.1 or higher and will be graded according to the National Cancer Institute of Common Terminology Criteria for AEs (CTCAE version 5.0).

AEs are defined as treatment emergent (TEAEs) if they onset or worsen (by investigator report of a change in intensity/severity), during the treatment emergent phase defined below. Worsening is determined by comparison with the pre-treatment severity of the AE recorded closest to the start of dosing.

When assigning AEs to the relevant phase of the study the following rules will apply:

- Pre-treatment phase – All AEs with a start date after signing the informed consent form (ICF), prior to the first administration of IP that do not subsequently go on to worsen during the treatment emergent phase.
- Treatment emergent phase – All AEs starting or worsening (severity) following the first administration of IP for the duration of the treatment period, up to and including 30 days after the last dose of study treatment as per the study safety follow-up period but prior to subsequent cancer therapy. AEs with a missing start time which occur on the same day as first IP administration are reported as treatment emergent. Note that the treatment emergent phase includes the on treatment and safety follow-up periods.
- Off-treatment phase – All AEs starting more than 30 days after last dose of study treatment or once subsequent cancer therapy is started, whichever is earlier.

Serious AEs (SAEs)

A SAE is any AE that:

- Results in death
- Is immediately life-threatening
- Requires inpatient hospitalization or prolongation of existing hospitalization
- Results in persistent or significant disability/incapacity
- Is a congenital anomaly/birth defect in offspring of the subject
- Is an important medical event that may jeopardize the subject.

AEs of Special Interest (AESIs)

The following are considered to be AESIs for AZD4573:

- Tumour lysis syndrome (TLS) (see [Section 4.11.12](#))
- Hepatotoxicity (including Potential Hy's Law (PHL), Drug-induced liver injury (DILI), and Bilirubin increase with transaminase increase (ALT or AST or both)).
- Neutropenia (including Febrile neutropenia, Neutropenic sepsis, and Neutrophil count decrease)
- Thrombocytopenia, including Platelet count decrease
- Myocardial ischaemia
- Pyrexia

The following are AESIs for acalabrutinib:

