4.11.6 Clinical Laboratory, Blood Sample

4.11.6.1 Definitions and Derivations

All local laboratory results collected will be listed (refer to Section 17.1.6, 17.1.7 and Section 10.2 of the CSP for the list of clinical safety laboratory tests to be performed and the SoA for timing and frequency).

Laboratory tests will be grouped according to chemistry, haematology, and coagulation. Listings will be provided for all laboratory results. Laboratory parameters will be assessed at baseline as well as throughout the study.

For chemistry and haematology parameters, laboratory abnormalities with toxicity grades according to the NCI CTCAE version 5.0 will be derived.

Laboratory variables that will be measured are detailed in Table 6.

Table 6: Laboratory Safety Variables

Haematology/Haemostasis (whole blood)	Clinical Chemistry (serum or plasma)	
B-Blasts	S-Albumin	S-C Reactive Protein
B-Blasts/Leukocytes	S-Alkaline Phosphatase (ALP)	S-Factor V Leiden
B-Hematocrit	S-Alanine Aminotransferase (ALT)	S-Gamma Glutamyl Transferase (GGT)
B-Hemoglobin	S-Aspartate Aminotransferase (AST)	S-Glucose
B-Leukocytes (white blood cell count)	S-Bicarbonate	S-Lactate Dehydrogenase (LDH)
B-Lymphocytes (ALC)	S-Direct Bilirubin	S-Magnesium
B-Lymphocytes/Leukocytes	S-Bilirubin (BILI)	S-Phosphate

B-Platelet	S-Indirect Bilirubin	S-Potassium
	S-Calcium	S-Protein
Coagulation	S-Cholesterol	S-Sodium
Activated partial thromboplastin time (APTT)/Prothrombin time (PT)	S-Creatine Kinase (CK or CPK)	S-Triglycerides
Prothrombin international normalized ratio (INR)	S-Chloride	S-Urate
D-dimer (where available at institution)	S-Creatinine	S-Urea Nitrogen
Fibrinogen	S-Creatinine Clearance	
Urinalysis (dipstick)		
U- Erythrocytes/Blood	U-Glucose	U-Protein
U-Ketones		

Abbreviations: B=blood; P=plasma; S=serum; U=urinalysis.

All values will be classified as low (below range), normal (within range), or high (above range) based on local laboratory reference ranges. Results will be converted to standard units. For assessments included in CTCAE version 5.0, the CTCAE grade will be calculated.

Liver Function Parameters

Subjects with elevated post-baseline ALT, AST, or Total Bilirubin will be identified. The number and percentages of these subjects will be tabulated.

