4.11.6.2 Presentations

All clinical laboratory results will be listed.

For all continuous laboratory assessments, absolute values, change from baseline will be summarised using descriptive statistics at each time point by dose level/cohort. Box plots of absolute values and change from baseline values for haematology and clinical chemistry parameters will also be presented.

For clinical haematology, clinical chemistry and coagulation endpoints, shift tables from baseline to worst on-treatment value according to reference range classification will be created. CTCAE grade changes from baseline to the maximum on-treatment grade will also be provided. In addition, the number of subjects with ≥ 2 CTCAE grade changes and CTCAE grade changes of 3 or 4 will be summarised by actual dose level/cohort for clinical chemistry and haematology parameters.

Liver Function Parameters

For subjects with “Potential Hy’s law”, the change in the following laboratory parameters from baseline to each post-baseline visit will be summarized: ALT, AST, ALP, GLDH, LDH, GGT, and INR. Individual subject data for these laboratory parameters will be listed as well.

Plots for both maximum post-baseline ALT and AST versus the maximum post-baseline BILI (expressed as multiples of their upper limit of normal [ULN] reference range) will be produced with reference lines at 3 x ULN for ALT and AST and 2 x ULN for total bilirubin.

Liver biochemistry test results over time for subjects with elevated ALT or AST ($\geq 3 \times$ ULN) and elevated bilirubin ($\geq 2 \times$ ULN,) regardless of whether or not these elevations occurred at the same visit, or ALT or AST of $\geq 5 \times$ ULN, will be tabulated and plotted.

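### Section 4.3.2 gives two incompatible windows for worst-value summaries, and the one ending on the last dose day drops later values from the laboratory and urinalysis shift tables

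*SAP*

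**What the plan says.** SAP Section 4.3.2 (Visit Window) has two statements on extreme values. One bullet says that summaries of maximum or minimum use the value "recorded on treatment (from the day of the first IP administration up to the day of the last IP administration". The last bullet, on choosing among several values in a visit window, adds that "in summaries of extreme values all post baseline values collected are used including those collected at unscheduled visits".

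Section 4.11.6.2 specifies for haematology, chemistry and coagulation that "shift tables from baseline to worst on-treatment value according to reference range classification will be created". It also plans CTCAE grade changes from baseline to the maximum on-treatment grade. Section 4.11.7.2 uses the worst on-treatment value for the urinalysis shift table.

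For adverse events, Section 4.11.4 runs the treatment-emergent phase "up to and including 30 days after the last dose of study treatment as per the study safety follow-up period", cut short by subsequent cancer therapy. It adds: "Note that the treatment emergent phase includes the on treatment and safety follow-up periods".

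**The concern.** The two rules in Section 4.3.2 differ at both ends. The first closes on the last day of study drug; the second has no end. The first opens on the day of first dose, so a pre-dose Day 1 value, which can be the baseline under Section 4.2, may enter as an on-treatment value. The second admits only post-baseline values. Two programmers following the same section could produce different shift tables.

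The first rule also has a consequence of its own. A count that reaches its lowest point, or a transaminase that peaks, after the final dose would be a treatment-emergent AE if reported, yet would be missing from the grade-shift table. Subjects taken off both drugs for toxicity are those whose worst value may well come after the last dose. Laboratory data belong to the primary endpoint of Module 1 Part A (Section 2.1), and thrombocytopenia, neutropenia and hepatotoxicity are AESIs for AZD4573 (Section 4.11.4), so these tables should agree with the AE tables on what period they cover.

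**Working it through.** The SAP states no figure for this, so the check compares the texts and then counts days.

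**Which outputs depend on the on-treatment wording**

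| Output | SAP section | Window as worded |
|---|---|---|
| Laboratory reference-range shifts | 4.11.6.2 | worst on-treatment |
| CTCAE grade shifts | 4.11.6.2 | maximum on-treatment |
| Urinalysis shifts | 4.11.7.2 | worst on-treatment |
| Counts of CTCAE grade changes of 2 or more, and of 3 or 4 | 4.11.6.2 | not stated |
| Elevated ALT, AST or bilirubin | 4.11.6.1 | post-baseline |
| ALT/AST against bilirubin plots | 4.11.6.2 | maximum post-baseline |
| QTcF outliers | 4.11.9 | following IP, no end date |
| AEs and AESIs | 4.11.4 | to last dose + 30 days |
| DLTs | 4.11.3 | as approved by the SRC |

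The first three rows are exposed. The SAP's only definition of on treatment for measured values is the Section 4.3.2 bullet. The term cannot be stretched to cover follow-up, because Section 4.11.4 names on treatment and safety follow-up as two parts of the treatment-emergent phase.

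**Days excluded by the first rule**

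Inputs:
- The window closes on the last IP day, L (Section 4.3.2).
- The treatment-emergent phase ends on Day L + 30 (Section 4.11.4).
- L = 85 is the final-dose day in the relative dose intensity example (Section 4.11.2).
- L = 29 is the day of the fifth weekly dose: 1 + 4 × 7 = 29.

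Assumptions: both drugs stop on Day L, and there is no death, data cut-off or subsequent cancer therapy before Day L + 30.

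Share excluded = 30 / (L + 30).

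- L = 29: 30 / 59 = 51%.
- L = 85: 30 / 115 = 26%.
- Limiting case, a single dose on Day 1: 30 / 31 = 97%. The window then closes before Day 2, where Section 4.3.2 opens the first post-baseline visit window.

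The share rises the earlier a subject stops. The second rule excludes none of these days.

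**Comparison with the exposure rule**

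Section 4.11.1 credits AZD4573 exposure for 6 days after the last infusion. With a last dose on Day 85, exposure ends on Day 91 (85 + 6) and the treatment-emergent phase on Day 115, while the first rule closes on Day 85. The SAP thus counts days as exposed for AZD4573 that its worst-value rule treats as off treatment.

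**The case against.** The strongest reply is that the two bullets can be read together. The note is attached to the rule that picks the value closest to the scheduled visit, so it may mean only that extreme-value summaries ignore that rule, while the earlier bullet sets the period. This reading is possible, but it does not rescue the plan. It requires the reader to narrow a note that refers to all post-baseline values collected. If accepted, it removes the contradiction and leaves the cut-off at the last dose fully in force for the shift tables.

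Several limits do stand:

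- The rule ends on the last IP day, not the last infusion. If acalabrutinib continues after AZD4573 stops, the window stays open and nothing is lost until acalabrutinib ends.
- A reader might infer that maximum ALT and bilirubin, or ECG extremes, are biased downwards generally. The SAP does not support this: its liver outputs are worded post-baseline and its QTcF outliers have no end date.
- A reader might count the 6 days after a Day 29 infusion as 6 of 35 Cycle 1 days (17%) lost for everyone. That holds only if both drugs stop on Day 29. The window is not per cycle, so a subject who continues loses nothing there.
- A reader might conclude that the error always runs towards fewer severe values. Closing the window early can only lower the worst post-dose value, but admitting a pre-dose Day 1 value can carry a baseline abnormality into the on-treatment worst value.
- A reader might add that Table 6 shows "B-Lymphocytes/Leukocytes" and platelets but no neutrophils, although the AESI list includes "Neutropenia (including Febrile neutropenia, Neutropenic sepsis, and Neutrophil count decrease". This is a separate question and is unproven here. The table is split across pages, Section 4.11.6.1 refers to the protocol for the test list, and the table is not exhaustive: GLDH (Section 4.11.6.2) and immunoglobulins (Section 4.11.14.1) are summarised without appearing in it.

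It is also true that the analyses are descriptive (no hypotheses are tested, Section 4.10.1) and that enrolment has been permanently halted (Section 4.12). That lowers the stakes without making the two rules agree.

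**Conclusion.** The point holds in a limited form. Section 4.3.2 as written gives two incompatible windows, and the narrower one removes post-treatment worst values from three sets of outputs: laboratory reference-range shifts, CTCAE grade shifts and urinalysis shifts. The effect falls on subjects who stop both drugs, and for those who stop because of toxicity it can understate the worst post-dose grade.

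Under the stated assumptions, just over half of the treatment-emergent days are excluded for a last dose on Day 29 and about a quarter for Day 85. These are shares of days, not of events; how many grade 3 or 4 values would be missed cannot be computed from the document. The wider claim, that AESI, DLT, liver or QTcF results are distorted, is not supported, because none of those outputs uses the on-treatment wording and all laboratory results are listed in any case.

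**What to change.** Replace the last-dose-day limit in Section 4.3.2 with one worst-value window used throughout: post-baseline values, with pre-dose Day 1 excluded and unscheduled values included, through 30 days after the last dose of study treatment and before subsequent cancer therapy. This matches the treatment-emergent phase in Section 4.11.4. Align the note at the end of Section 4.3.2 with it, and use the same term in Sections 4.11.6.2 and 4.11.7.2, including for the CTCAE grade-change counts whose window is not stated.

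The cost is SAP wording and one derivation flag. No further data need to be collected for the change. Reported worst grades may become slightly less favourable.
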